7.11. Study Week 24 (Day 169 +/- 3 days) - Continuing Subjects Only

The Study Week 24 visit should occur within \pm 3 days of the scheduled date. During this visit, the following study procedures will be performed:

- An abbreviated, symptom-directed physical examination
- Vital signs (weight, temperature, blood pressure, heart rate) after at least 3 minutes of rest
- 12 Lead ECG after at least 3 minutes of rest, will be recorded and assessed for any clinically significant abnormality
- The date and time of the last dose of CCX140-B prior to collection of the PK sample will be recorded
- Blood samples will be collected before dose administration for serum chemistry (including coagulation panel and lipids), hematology, serum pregnancy test (in women of childbearing potential), PK (time 0 only), plasma MCP-1, and PD (including lymphocyte subset) measurements; record the time of blood collection
- **Process the first morning void urine sample collection for quantitative urinalysis, UPCR, UACR, Cystatin C, Urine MCP-1, MCP-1/creatinine ratio and urine PD assessment**
- **Process the 24-hour urine sample collection for quantitative urinalysis, UPCR, UACR, Cystatin C, Urine MCP-1, MCP-1/creatinine ratio urine PD assessment and urine protein excretion/day**
- Subjects will be asked to complete the SF-36 v2 and EQ-5D-5L. The ACTG Brief Peripheral Screening Tool will be administered
- If the subject has not yet taken the morning dose of CCX140-B for this day, the subject will be asked to take the dose
- Drug accountability and reconciliation with subject completed diaries
- Any changes in concomitant medication use will be recorded
- Any adverse events will be recorded
- **Provide subject with container for collection of first morning void on the morning of the next visit**
- After all study procedures have been completed, the subject will be reminded to:
 - Come to the study center for the Week 28 follow-up visit
 - Return all used and unused containers of study medication along with completed diaries for final drug accountability

- **On the morning of the next visit, collect the first morning void and refrigerate until it is brought to the study center**

7.12. Follow Up visit - Study Week 16 (Day 114 +/- 3 days for discontinuing subjects) and Week 28 (Day 197 +/- 3 days for continuing subjects) - (See Section 7.13 for PK elimination guidelines)

The follow-up visit should occur within \pm 3 days of the scheduled date. During this visit, the following study procedures will be performed:

- An abbreviated, symptom-directed physical examination
- Vital signs (weight, temperature, blood pressure, heart rate) after at least 3 minutes of rest
- 12 Lead ECG after at least 3 minutes of rest, will be recorded and assessed for any clinically significant abnormality
- Blood samples will be collected for serum chemistry (including coagulation panel and lipids), hematology, serum pregnancy test (in women of childbearing potential), PK (time 0 only), plasma MCP-1, and PD (including lymphocyte subset) measurements; record the time of blood collection
- **Process the first morning void urine sample collection for quantitative urinalysis, UPCR, UACR, Cystatin C, Urine MCP-1, MCP-1/creatinine ratio and urine PD assessment**
- Subjects will be asked to complete the SF-36 v2 and EQ-5D-5L.
- The ACTG Brief Peripheral Screening Tool will be administered
- Any changes in concomitant medication use will be recorded
- Any adverse events will be recorded

7.13. PK Elimination Visits

Upon discontinuation of treatment for any reason, **including end of study**, a sample of whole blood should be collected for assessment of elimination at 2, 7 and 14 days after discontinuation. Record the time of blood collection.

After all study procedures have been completed, the subject will be discharged from the study. The subject's condition will be evaluated by the Investigator at the end of the clinical trial (Week 28) and appropriate standard of care medical treatment **should be implemented for** all subjects as needed.

7.14. Early Termination Visit (See Section 7.14 for PK elimination guidelines)

If a subject will be withdrawn early from the study, the following termination procedures should be completed whenever possible:

- **Whenever possible, the subject will be asked to collect all urine for the 24 hours after the last dose of study drug.**

- An abbreviated, symptom-directed physical examination
- Vital signs (weight, temperature, blood pressure, heart rate) after at least 3 minutes of rest
- Blood samples and urine will be collected for shipment to the central laboratory for serum chemistry, hematology, serum pregnancy test (in women of childbearing potential) and quantitative urinalysis
- Need for dialysis will be recorded
- **If available, process the first morning void urine sample collection for UPCR and UACR assessment**
- **If available, process the 24-hour urine sample for quantitative urinalysis, UPCR, UACR, Cystatin C, Urine MCP-1, MCP-1/creatinine ratio urine PD assessment and urine protein excretion/day**
- 12 Lead ECG after at least 3 minutes of rest, will be recorded and assessed for any clinically significant abnormality
- Drug accountability and reconciliation with subject completed diaries
- Any changes in concomitant medication use, including plasma therapy regimen, will be recorded
- Any adverse events will be recorded. If an adverse event remains unresolved at the conclusion of the study, a clinical assessment will be made by the Investigator and the Sponsor's Medical Monitor to determine whether continued follow-up of the adverse event is warranted
- A final safety follow-up visit will be scheduled for 4 weeks after subject discontinues study drug

8. STUDY ASSESSMENTS

8.1. Efficacy Assessments

8.1.1. Urinary Measurements

Efficacy will be evaluated by assessment of urine protein:creatinine ratio (UPCR), urine albumin:creatinine ratio (UACR), and estimated glomerular filtration rate (eGFR) using the CKD-EPI Cystatin C equation, CKD-EPI Creatinine equation, CKD-EPI Creatinine-Cystatin C equation and MDRD Creatinine equation assessed at Weeks 12 and 24.

The urine samples, first morning void and 24-hour urine sample will be sent to the central laboratory for analysis. The following analyses will be performed according to the [Time and Events Table](#):

- Urine protein to creatinine ratio (UPCR): the urine protein creatinine ratio is the ratio of the urine protein concentration to the urine creatinine concentration
- Urine albumin to creatinine ratio (UACR): the urine albumin creatinine ratio is the ratio of the urine albumin concentration to the urine creatinine concentration Urinalysis including

blood, protein, and nitrites; if positive for blood, protein, or nitrites, a microscopic assessment for RBC casts and RBC count will be performed;

Microscopic review is triggered if a urinary dipstick test is positive for blood, nitrite, or protein. When microscopy is performed, hematuria will be categorized as follows: None, Occasional (Occ), 1 - 2, 3 - 5, 6 - 9, 10 - 15, 16 - 29, 30 - 49, 50 - 75, and >75 RBCs per high power field.

8.1.2. Estimated Glomerular Filtration Rate

The estimated glomerular filtration rate (eGFR) will be calculated at all applicable study visits using the CKD-EPI Creatinine-equation ([Schwartz GJ, et al. 2016, Selistre L et al 2016](#)), the CKD-EPI Cystatin C ([Dhamidharka VR, et al, 2002](#)) equation the CKD-EPI Creatinine- Cystatin C equation ([Stevens et al., 2008](#)) and the MDRD Creatinine equation ([Levey et al. 1999, Levey et al. 2006](#)).

8.1.3. Serum Albumin

The serum albumin level provides an index of the degree of protein loss. Hypoalbuminemia may be seen in subjects with severe proteinuria and the nephrotic syndrome.

8.1.4. Health-Related Quality of Life and ACTG BPNST Assessments

The SF-36 v2 and EQ-5D-5L and ACTG BPNST will be completed by study subjects at visits specified in the [Time and Events Table](#) to measure changes from baseline in health-related quality of life and the ACTG BPNST will be completed by the study subject and the study doctor to assess changes in neuropathy. Proven translations will be used for non-English speaking subjects, whenever possible. An administrator will facilitate completion of the SF-36 and EQ-5D-5L questionnaires by the subjects, but will not complete the forms for the subjects. The administrator will establish a rapport with the subject, emphasize the importance of completing the form, and serve to answer questions and address concerns. The questionnaires should be completed by subjects before seeing the Investigator at the visit.

8.2. Safety Assessments

8.2.1. Physical Examinations, Vital Signs, and ECGs

A complete physical examination (including evaluation of general appearance/mental status, HEENT [head, eyes, ears, nose, throat], and the following body systems: dermatologic, cardiovascular, respiratory, gastrointestinal, musculoskeletal and neurologic) for safety, assessments will be performed at visits indicated in the [Time and Events Table](#).

Body weight will be measured as part of the physical examinations. Height needs to be recorded at screening only. BMI will be calculated from the body weight and height measurements.

Vital signs will be measured during screening and on each scheduled study day as indicated in the [Time and Events Table](#). Blood pressure, pulse rate, and body temperature will be measured. All vital signs assessments will be performed after the subject has rested for at least three minutes, while subject is seated.

A baseline 12-lead ECG, after resting for at least 3 minutes, will be performed at screening and assessed for any clinically significant abnormalities. All abnormalities will be recorded in the

EDC system. Assuming the ECG abnormality does not preclude study entry, an ECG may be repeated as clinically indicated.

8.2.2. Clinical Safety Laboratory Assessments

The following tests will be performed at the visits identified in the [Time and Events Table](#).

- Hematology: hemoglobin, hematocrit, RBC count, WBC count with differential, platelet count, mean cell hemoglobin, mean cell hemoglobin concentration, mean corpuscular volume, reticulocyte count **and schistocytes**;
- Serum Chemistry: liver panel (total, direct **and indirect** bilirubin, lactate dehydrogenase [LDH], AST, ALT), renal panel (BUN, creatinine), creatine phosphokinase (CPK), albumin, sodium, potassium, magnesium, bicarbonate, chloride, calcium, inorganic phosphorus, glucose, total protein, alkaline phosphatase, uric acid, serum amylase, serum lipase, and cystatin C; at specified visits, coagulation panel (PT, PTT, INR), lipid panel (HDL, LDL, Triglycerides, Total Cholesterol) will be included
- Urinalysis: At the central laboratory, nitrite, blood, and protein, will be tested. If positive, microscopy will be performed;
- Virology (measured only at screening): hepatitis B surface antigen, hepatitis C antibodies, HIV 1 and 2 antibodies; virology tests done within 6 weeks prior to screening are acceptable for eligibility assessment;
- TB screen: Only interferon γ release assay (IGRA) done within 6 weeks prior to screening is allowed for eligibility assessment.

8.2.3. Adverse Events

An adverse event (AE) is defined as any untoward medical occurrence associated with the use of a drug in humans, whether or not considered drug related. An adverse event could therefore be any unfavorable and/or unintended sign (including abnormal laboratory findings), symptom, or disease temporally associated with the use of the drug, whether or not considered related to the drug. This definition includes intercurrent illnesses or injuries, and exacerbation of pre-existing conditions.

An unexpected adverse event is an adverse event that is not identified in nature, severity, or frequency in the current Investigator's Brochure, or that is of greater severity than expected based on the information in the Reference Safety Information listing within the Investigator's Brochure.

All adverse events occurring in subjects who have been randomized to treatment will be recorded in the EDC system and will be reported in accordance with regulatory requirements. Adverse events reported prior to commencement of administration of study medication will be considered pre-treatment events. If subject stops taking CCX140-B/placebo, adverse event reporting should be continued as long as study is active.

All adverse events will be monitored until resolution or, if the adverse event is determined to be chronic, until a cause is identified. If an adverse event remains unresolved at the conclusion of the study, a clinical assessment will be made by the Investigator and the Sponsor's Medical Monitor to determine whether continued follow-up of the adverse event is warranted.

8.2.3.1. Adverse Event Severity Assessment

The severity of each adverse event will be determined by the investigator using the following scale:

- Mild (Grade 1): no limitation of usual activities
- Moderate (Grade 2): some limitation of usual activities
- Severe (Grade 3): inability to carry out usual activities
- Life-threatening (Grade 4): an immediate risk of death
- Death (Grade 5)

8.2.3.2. Causality Assessment

The relationship of study drug (CCX140-B/placebo) to an adverse event will be determined by the Investigator and Sponsor based on the following definitions:

- Probably Not Related: the adverse event was more likely explained by causes other than study drug (CCX140-B/placebo).
- Possibly Related: there is evidence for a reasonable possibility that study drug (CCX140-B/placebo) administration caused the adverse event.

8.2.3.3. Serious Adverse Events

A serious adverse event (SAE) is defined as any untoward medical occurrence that at any dose:

- Results in death;
- Is life-threatening (i.e., the subject was, in the opinion of the Investigator, at immediate risk of death from the event as it occurred);
- Requires or prolongs hospitalization;
- Results in persistent or significant disability or incapacity;
- Is a congenital anomaly or birth defect;
- Is an important and significant medical event that, based on appropriate medical judgment, may jeopardize the subject and/or may require medical or surgical intervention to prevent one of the other outcomes defining serious.

Elective surgery already known during screening to occur in the course of the study, and elective hospitalizations for convenience of the subject which are clearly unrelated to any medical condition, and agreed upon between the Investigator and the subject, will not have to be reported as SAEs. Hospital stays on the evening of Day 1 (or beyond) will also not be considered an SAE, unless other SAE criteria are met.

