- **The subject will be given instructions and supplies for the urine collections on the day before the next visit (kit for first morning void and jug for 24-hour urine collection)**
 - **Collect the first morning void the day before the first visit (Day 0) and put in the smaller container.**
 - **Collect all urine for 24 hours starting AFTER the first morning void, including first morning void on the day of the Study Day 1 visit, in the big jug.**
 - **Keep specimens refrigerated until they are brought to the site at the Study Day 1 visit.**

7.2. Study Day 1

If eligible for the study, the subject will visit the study center on Day 1. The following procedures will be performed before taking the first dose of CCX140-B:

- A complete physical examination
- Vital signs (weight, temperature, blood pressure, heart rate after at least 3 minutes of rest)

- A 12-lead ECG, after at least 3 minutes of rest, will be recorded and assessed for any clinically significant abnormality
- Blood samples will be collected for serum chemistry (including coagulation panel and lipids), pregnancy test (in women of childbearing potential), hematology, DNA, plasma MCP-1, PK, PD (including lymphocyte subsets) and baseline measurements
- **Process the first morning void urine sample collection for quantitative urinalysis, UPCR, UACR, Cystatin C, Urine MCP-1, MCP-1/creatinine ratio and urine PD assessment**
- **Process the 24-hour urine sample collection for quantitative urinalysis, UPCR, UACR, Cystatin C, Urine MCP-1, MCP-1/creatinine ratio urine PD assessment and urine protein excretion/day**
- Any pre-treatment adverse events (from time of the screening visit) will be recorded
- Subjects will be asked to complete the SF-36 v2 and EQ-5D-5L
- Subjects will be asked to complete their diary each day immediately after each dose
- The ACTG Brief Peripheral Neuropathy Screening Tool will be administered

Once deemed eligible, the following procedures will be performed:

- Study medication (in kits, containing 4-week supply bottles of CCX140-B/Placebo), will be provided to the subject with dosing instructions
- The subject will be asked to take the first dose of CCX140-B while at the study center and should remain at the study center for observation at the PI's discretion
- The time of the dosing of CCX140-B will be recorded

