- PK blood samples will be collected at **Time 0 (pre-dose)**, 0.5, 1, 2, 3, 4, and 6 hours following CCX140-B or placebo dosing for plasma CCX140 concentration measurements; the actual time of each blood sample collection will be recorded
- A blood sample will be collected for pharmacodynamic marker measurements
- Any changes in concomitant medication use will be recorded
- Any post-dosing adverse events will be recorded
- **Provide the subject with the kit for collection of the first morning void**
- After all study procedures have been completed, the subject will be reminded to:
 - Come to the study center for the Week 1 study visit
 - Store the study medications in a cool and dry place according to label instructions for the duration of the study
 - **On the morning of the next visit, collect the first morning void in the container provided and refrigerate until it is brought to the study center**

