9.2.4. Safety Endpoints include

- Subject incidence of treatment-emergent adverse events, adverse events leading to study withdrawal, and serious adverse events;
- Change from baseline and shifts from baseline in all safety laboratory parameters;
- Change from baseline in vital signs;
- Change from baseline in score on the ACTG BPNST
- Clinically significant abnormal ECG findings
- Physical examinations

Treatment-emergent adverse events (TEAE) will be summarized for each treatment group by MedDRA System Organ Class (SOC) and preferred term (PT), by relatedness and maximum severity. Treatment-emergent serious adverse events (TESAE) and TEAE leading to study withdrawal will be separately listed and may be summarized if warranted by the subject incidences.

Vital signs and laboratory test results, and their changes from baseline will be summarized by treatment group and visit. Abnormal laboratory values will be flagged in the data listing. Shift tables will be generated by study visit.

Individual ECG findings and change from baseline in ECG findings will be listed by treatment group, subject, and study visit, and summarized by treatment group and visit.

Findings from physical examinations will be listed.

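### The Day 1 hospital-stay exemption has no end date and no limit by purpose or cause, and conflicts with the hospitalisation criterion in the same SAE definition

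*Protocol*

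**What the plan says.** Protocol Section 8.2.3.3 opens with a threshold: "A serious adverse event (SAE) is defined as any untoward medical occurrence that at any dose". A list of alternative criteria follows, and one of them is "Requires or prolongs hospitalization". Another rests on judgment: "Is an important and significant medical event that, based on appropriate medical judgment, may jeopardize the subject".

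Two exemptions close the section. The first covers elective surgery already known at screening and "elective hospitalizations for convenience of the subject which are clearly unrelated to any medical condition", the latter also agreed between investigator and subject. The second reads: "Hospital stays on the evening of Day 1 (or beyond) will also not be considered an SAE, unless other SAE criteria are met".

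Protocol Section 7.2 describes Day 1. The subject takes the first dose at the site and "should remain at the study center for observation at the PI's discretion". PK samples are taken before dosing and at "0.5, 1, 2, 3, 4, and 6 hours following CCX140-B or placebo dosing for plasma CCX140 concentration measurements". No overnight stay is scheduled.

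Protocol Section 9.2.4 names as a safety endpoint "Subject incidence of treatment-emergent adverse events, adverse events leading to study withdrawal, and serious adverse events". SAP Section 3.6.1 tabulates treatment-emergent serious events, and the SAP gives no seriousness definition of its own.

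**The concern.** The second exemption lacks the limits of the first. The elective exemption depends on the stay being planned or unrelated to a medical condition. The Day 1 exemption does not mention purpose or cause, and 'or beyond' has no stated end. Because it yields only to other SAE criteria, hospitalisation itself is set aside for any stay it covers.

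Several things follow from this classification. SARs and SUSARs are defined as subsets of SAEs (Protocol Section 8.2.3.4), so an event not classed as serious cannot become either. It would not enter 24-hour reporting (Protocol Section 8.2.5) or the treatment-emergent SAE tables (SAP Section 3.6.1). Safety and tolerability form the primary safety objective (Protocol Section 3.1). Infection and haemolysis are among the events of special interest (Protocol Section 4), and either can lead to admission. With about 40 sites planned, an unclear rule may also be applied differently from site to site.

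**Working it through.** The check is textual, because the plan gives no figure to reproduce. The closing sentence can be read in two ways:

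- **Literal reading:** any hospital stay on the evening of Day 1 or at any later time is exempt unless another criterion is met.
- **Narrower reading:** a stay that begins on the evening of Day 1 is exempt, even if it runs on past that evening.

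The table applies the list of criteria alone, and then each reading, to four cases. In the cases with an untoward event, hospitalisation is the only criterion met.

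| Case | Criteria list alone | Narrower reading | Literal reading |
|---|---|---|---|
| Admission for an untoward event after screening and before Day 1 evening | SAE | SAE | SAE |
| Day 1 overnight stay for observation only, no untoward event | Not an SAE | Not an SAE | Not an SAE |
| Day 1 overnight stay required by a first-dose reaction | SAE | Exempt | Exempt |
| Admission for an untoward event some weeks into treatment | SAE | SAE | Exempt |

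1. **First row.** SAE reporting starts at screening (Protocol Section 8.2.5), so the hospitalisation criterion works normally until the evening of Day 1 on either reading.
2. **Second row.** A stay with no untoward occurrence fails the threshold of the definition. It is not an SAE with or without the exemption, so here the sentence only clarifies.
3. **Third row.** Here the sentence changes a classification on both readings. The last Day 1 PK sample is at 6 hours and no overnight stay is planned, so a stay that night is unscheduled and could be prompted by the first dose. The protocol looks for early harm in that interval, with blood count and bilirubin at 2 and 6 hours after dosing (Time and Events Table, footnote 3).
4. **Fourth row.** The readings part here. Reporting runs to 28 days after the last dose. On the literal reading the exemption would therefore span about 84 + 84 + 28 = 196 days for a subject who completes the extension, and about 84 + 28 = 112 days for one who stops at Week 12. On the narrower reading it reaches only stays that begin on one evening per subject.

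Nothing elsewhere in the protocol or the SAP says which reading applies.

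The number of affected events cannot be calculated, because the documents give neither an SAE rate nor a hospitalisation rate. What follows from the design is the effect of a single case: with 10 subjects per arm, one subject reclassified from SAE to no SAE changes that arm's SAE incidence by 1/10, or 10 percentage points.

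**The case against.** The strongest reply is that the narrower reading is the sensible one. The sentence continues a list of logistical stays. If every later admission were meant, there would be no reason to name the evening of Day 1, and the elective exemption just before it would be largely redundant. Open-ended observation after the first dose (Protocol Section 7.2) explains why such a sentence was written. The sentence also speaks of stays rather than events, so it might mean only that a stay by itself is not an SAE.

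There are also safeguards. The important-medical-event criterion remains, and an infection or haemolysis leading to admission is a natural candidate for it. All adverse events in randomised subjects are recorded whether serious or not (Protocol Section 8.2.3). The DMC reviews unblinded safety data (Protocol Section 6.5.3).

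Much of this stands. The narrower reading is the likelier intent, and the exposure is in classification and expedited reporting rather than in detecting the event. The reply does not remove the problem, for three reasons:

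- The narrower reading still exempts a Day 1 stay caused by a first-dose reaction.
- If the sentence meant only that a stay alone is not an SAE, it would add nothing to the threshold already in the definition. Its reference to other criteria instead suggests that hospitalisation has been set aside.
- The important-medical-event criterion replaces an objective trigger with site judgment.

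A reader might go further and infer that the sentence cancels the hospitalisation criterion and that SAEs will be under-counted. The documents do not support that. The criterion operates before the evening of Day 1 on either reading, and for later admissions on the narrower one. An under-count is a possible consequence, not a demonstrated one.

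**Conclusion.** The point holds as a conflict within Protocol Section 8.2.3.3 that the documents leave unresolved. The exemption is open-ended in time and silent on purpose and cause, and on both readings it can remove an event that the hospitalisation criterion would capture. The literal reading affects events serious only through hospitalisation from the evening of Day 1 to the end of SAE reporting. The likelier reading affects only stays beginning on the evening of Day 1, including any caused by the first dose.

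The consequence is a risk of non-serious or inconsistent classification, with loss of 24-hour reporting, SUSAR assessment and inclusion in the SAE tables. Its frequency cannot be estimated, and any figure would rest wholly on assumed rates. The conclusion needs no numerical assumption, only that some sites would follow the sentence as written. It warrants correction because it concerns a stated rule on which expedited reporting depends.

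**What to change.** Amend Protocol Section 8.2.3.3 in three respects:

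- Delete 'or beyond'.
- Limit the exemption to a Day 1 stay arranged solely for protocol observation or PK sampling and not prompted by an adverse event.
- State that any stay required or prolonged by an untoward event is judged by the listed criteria.

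Suitable wording would be: *An overnight stay on Day 1 that is arranged only for protocol observation or PK sampling, and is not prompted by an adverse event, is not an SAE. Any stay required or prolonged by an untoward event is assessed against the criteria above.*

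For subjects already treated, check recorded adverse events that involved a hospital stay against the corrected definition before database lock, so that the SAP Section 3.6.1 tables use one rule throughout. Any event reclassified as serious should then go through the reporting and SUSAR assessment steps in Protocol Sections 8.2.5 and 8.2.3.4.

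The cost is a short rewording by amendment, a notice to sites and one pre-lock review. No new assessment is needed. The documents do not say whether the adverse event form records hospital stays for non-serious events; if it does not, the review would need a query to sites. The change is correct whichever reading was intended.
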